#### **2.4. Overall study design**

Both trials (“short-stay” and “same-day” surgery cohorts) will test the same hypothesis, and have the same protocol aims, inclusion and exclusion criteria, procedures, assessments, methods of data analysis, and hypothesis testing, but are otherwise separate (and separately analyzed). Two cohorts are studied because their operations may have different pain intensities and opioid requirements. The protocol is very similar (hypothesis, aims, inclusion/exclusion, procedures, assessments, data analysis, hypothesis testing) to that of the dose-finding Pilot (Preliminary Studies). In each cohort, patients will be randomized to general anesthesia with methadone or short-duration opioids. Patients are followed in-hospital, then queried daily for 30d after discharge through emailed REDCap or paper surveys. Additional REDCap surveys will be emailed at 6 and 12mo.

Target enrollment is 300 evaluable subjects per cohort (150 control, 150 methadone). A 25% overall drop-out rate prior to 30d follow-up is conservatively assumed, thus 375 subjects in each cohort will be studied (750 total).

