### 2.7 Sample size justification

Sample size is based on the primary outcome measure, total 30d post-discharge home opioid use (number of opioid tablets). Based on available reports (Background) and the Preliminary Results, an ideal state of post-discharge opioid use is defined as  $\leq 5$  pills in 30 days. In the Preliminary data, the rate of "high" post-discharge opioid use (defined as  $> 5$  pills in 30d) was 45% in the short-duration opioid group. With a conservative assumption of a relative risk of 65% for the long-duration group (30% rate of "high" opioid use), a total of 300 subjects (150 per group) will be needed to achieve 80% power assuming alpha = 0.05.

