### **3.0 Recruitment strategy and feasibility**

Subjects will be 18-65 yr. Because this is the first evaluation of methadone for outpatient anesthesia, children and older patients will not be studied (because of declining methadone elimination and increased risk of respiratory depression with age). Such studies may ensue after safety is established in the present investigation. Sample size calculations show that 300 evaluable (completing 30d follow-up) patients are needed in each of the 2 study cohorts (600 total). Change in scheduled operation, prolonged ( $>1$ d) stay of scheduled short-stay (next day discharge) patients, unanticipated admission of same-day patients, or patient withdrawal has occurred in  $\sim 10\%$  of our study patients to date. This, combined with post-op loss to follow-up (see below), suggests a potential overall drop-out rate before completion of 30d follow-up of  $<15\%$ . Hence, to ensure 300 pts evaluable at 30d, a conservative 25% drop-out is estimated and 375 pts in each of the 2 study cohorts will be randomized (750 total). The Duke Department of Anesthesiology provides anesthetics for  $>66,000$  procedures per year. The main campus of Duke University Health System includes Duke University Hospital which is a 957 bed facility. In 2016 there were 41,408 patients admitted and 1,119,151 outpatient visits. Duke University Hospital includes the Duke North Hospital/Duke Medical Pavilion ( $\sim 54$  ORs), the Children’s Health Center, the Duke Eye Center (6 ORs), and Ambulatory Surgery Center (9 ORs). Between the Duke North Hospital/Duke Medical Pavilion and Ambulatory Surgery Center there were 34,492 anesthetics performed in 2017. These included, for example, 375 laparoscopic cholecystectomies and 269 laparoscopic hysterectomies  $\pm$  salpingoophorectomies, further supporting specific feasibility. If enrollment lags, or for strategic advantage, Duke Regional and/or Duke Raleigh Hospitals can be added as future sites.

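### Section 2.7 prints a 30% methadone rate that does not match its relative risk of 65% and does not give 80% power; separately, 375 randomised with 25% loss leaves 281 evaluable, not 300

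*Combined protocol and SAP*

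**What the plan says.** Section 2.7 sizes each cohort on the proportion of patients who take more than 5 pills in 30 days. In the pilot data this proportion "was 45% in the short-duration opioid group". The effect assumption is given twice in one sentence, first as a ratio and then, in parentheses, as a rate of high use: "With a conservative assumption of a relative risk of 65% for the long-duration group (30% rate of". The conclusion is that "a total of 300 subjects (150 per group) will be needed to achieve 80% power assuming alpha = 0.05". Whether alpha is one- or two-sided, and which formula was used, is not stated. Section 2.8 names the chi-square test for this comparison and analyses the two cohorts separately.

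Section 2.4 carries the number forward: "Target enrollment is 300 evaluable subjects per cohort (150 control, 150 methadone". It then assumes 25% loss before day 30 and arrives at 375 per cohort. Section 3.0 repeats this with the aim of securing 300 evaluable at 30 days: "a conservative 25% drop-out is estimated and 375 pts in each of the 2 study cohorts will be randomized (750 total". The same section expects actual overall drop-out to be below 15%. The synopsis gives the same totals: 600 evaluable from 750 studied, with 25% loss.

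**The concern.** A reader who checks section 2.7 would naturally enter the two printed rates, 45% and 30%, because the planned test compares two proportions. That does not return 80% power at 150 per group. The gap between 30% and the 29.25% implied by the relative risk is only 0.75 percentage points, but it moves the required size by 32 per cohort and carries the power across the 80% line.

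The step from 300 to 375 has its own slip. Adding 25% to the target is not the same as allowing for 25% loss, so the plan's own drop-out rate does not leave the 300 that the power statement needs.

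Each cohort is a separate trial resting on this one calculation. If a cohort gives a null result, it will be set against the stated 80%, so that figure should be one that the printed inputs support.

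**Working it through.** **Inputs.** Control rate 45%, relative risk 65%, methadone rate 30%, 150 per group, alpha 0.05 and 80% power (all section 2.7); 1:1 allocation (2.4); chi-square test (2.8); 375 randomised and 25% loss (2.4, 3.0). Assumed, because not stated: two-sided alpha and no continuity correction.

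**Do the two effect sizes agree?** 0.65 × 45% = 29.25%. In the other direction, 30% / 45% = 66.7%.

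**Formulas** (pooled-variance two-proportion test, p̄ the mean of the two rates, n per group):

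- n = [1.960·√(2p̄(1−p̄)) + 0.842·√(p₁(1−p₁)+p₂(1−p₂))]² / (p₁−p₂)²
- power = Φ{[(p₁−p₂) − 1.960·√(2p̄(1−p̄)/n)] / √[(p₁(1−p₁)+p₂(1−p₂))/n]}

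**The plan's figure, from the relative risk (45% vs 29.25%).** p̄ = 0.37125.

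- n = (1.960 × 0.6833 + 0.842 × 0.6741)² / 0.1575² = 146.5, so 147 per group (294 per cohort).
- Power at 150 = Φ[(0.1575 − 1.960 × 0.05579) / 0.05504] = Φ(0.875) = 80.9%.

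The stated 150 per group and 80% reproduce.

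**From the printed pair (45% vs 30%).** p̄ = 0.375.

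- n = (1.960 × 0.6847 + 0.842 × 0.6764)² / 0.15² = 162.3, so 163 per group (326 per cohort).
- Power at 150 = Φ[(0.15 − 1.960 × 0.05590) / 0.05523] = Φ(0.732) = 76.8%.

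Exact enumeration of the uncorrected chi-square at 150 per group gives the same 80.9% and 76.8%.

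**Does another method rescue 30%?** At 45% vs 30% and 150 per group, the other two-sided methods tried give 73.0% (continuity-corrected or Fisher) to 77.5% (unpooled). None reaches 80%. One-sided 0.05 would need 128 per group, so it does not explain 150 either.

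**Drop-out.** 300 × 1.25 = 375, which is the plan's number. To keep 300 after 25% loss takes 300 / 0.75 = 400. Starting from 375:

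| Loss | Evaluable per cohort | Power at 29.25% | Power at 30% |
|---|---|---|---|
| 25% | 375 × 0.75 = 281 | 78.3% | 74.1% |
| 20% | 375 × 0.80 = 300 | 80.9% | 76.8% |
| 15% | 375 × 0.85 = 319 | 83.2% | 79.3% |

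**The case against.** The strongest reply is that the named assumption is the relative risk, that the 30% is only a parenthetical gloss on it, and that the relative risk supports the stated size and power. That stands. A reader might infer from the printed 30% that the 80% is a miscalculation and the trial is mis-sized; the documents do not support this.

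Nor do they establish that the printed figures are irreconcilable. All are whole percentages, and the 45% is a pilot rate that was probably rounded. As an illustration only, since no unrounded rates are given, 45.1% vs 29.5% is a relative risk of 0.654. It would print as 45%, 30% and 65%, and it gives 80.1% power at 150 per group. So rounding may explain the mismatch. What remains is that the reader cannot tell which rate was used, and that the pair as printed does not return the stated power.

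The mismatch is also small beside the uncertainty in a rate taken from pilot dose groups of typically about 20 (section 2.2). This limits its importance, but it does not make the printed figures agree.

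On drop-out, section 3.0 calls 25% conservative and expects less than 15%, and at 15% more than 300 remain. Section 2.8 also says that the analysis will not be confined to completers, so 281 need not be the number analysed. Both points ease the concern. Neither makes 375 with 25% loss equal 300, which is the sum that sections 2.4 and 3.0 rely on. The estimated enrolment of 1,000 in the synopsis does not close the gap either, because the synopsis still takes 600 evaluable from 750 studied with 25% loss.

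**Conclusion.** Two small, checkable inconsistencies stand.

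1. Section 2.7 prints an effect size in two forms that do not match as printed. The stated power holds for the relative risk (80.9% at 150 per group) and not for the printed 30% rate (76.8%). The difference is about 4 points of power, or 32 patients per cohort in required size.
2. The allowance for loss is 19 short per cohort at the plan's own 25% (281 against 300). Power is then below 80% on either rate: about 78% or 74%.

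The lowest figure, 74%, combines the less favourable rate with the heavier loss and should not be read as the expected power. At 15% loss, power is about 83% (29.25%) or 79% (30%).

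A reader might conclude that the trial is underpowered or must enrol more; the documents do not show that. The results assume two-sided alpha 0.05 and an uncorrected chi-square test. With a continuity correction, power at 150 per group would be 77.5% for 29.25% and 73.0% for 30%, which is a further reason to state the test behind the figure.

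**What to change.** In section 2.7, print the rate that was actually used, with its power: either 29.25% with about 81% at 150 per group, or 30% with about 77%. State in the same place that alpha is two-sided, if it is, and which test the calculation assumes.

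In sections 2.4 and 3.0, do one of the following:

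- state that 375 randomised with 25% loss yields about 281 evaluable per cohort, with power of about 78% (74% if 30% is the design rate); or
- state that 375 yields at least 300 evaluable only if drop-out is 20% or less, and refer to the expectation of less than 15%.

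Bring the matching line in the synopsis into agreement. The cost is protocol wording only. Enrolment, conduct and analysis do not change, and the one drawback is that some stated power figures become slightly less favourable.

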### 2.8 Hypothesis testing

For all Aims, the two cohorts ("short-stay" and "same-day" surgery) are analyzed separately. Subgroup analysis may also explore specific surgical procedures (procedure-specific analgesia).

Aim 1: Compare the influence of methadone vs short-duration opioids on short-term (before discharge) and intermediate term (1-30d post-discharge) opioid consumption.

30d post-discharge opioid use ( $> 5$  pills) will be compared between arms using Chi-square tests and multiple logistic regression, with opioid group as a predictor and adjusting for the important clinical and demographic covariates. Total pill consumption will be compared using GEE model with Poisson link function. In addition, a time-to-event (survival) model will be fit to compare time to opioid discontinuation between the two groups.

adjusting for the appropriate covariates. Opioid use during intraop, in-hospital post-op, and post-discharge periods will be evaluated using appropriate model and data transformation, depending on the distribution of the data. It is common in some analgesic trials that subjects dropping from different treatment groups differ with respect to reasons for early discontinuation (i.e. not random but outcome-related). Therefore analysis will not be “completers only”. Drop-out rates will be compared between the drug groups, and 30d opioid consumption ( $>5$  vs  $\leq 5$  pills) analyzed with and without drop-outs. Drop-outs will be censored at the time of dropping out in time to discontinuation analysis. A corollary of opioid consumption by patients is opioid prescribing by surgeons. It is possible that surgeons’ prescribing practices (# tablets per patient) may change during the study (coincidentally or as a result thereof) and this will be explored.

**Aim 2:** Compare methadone vs short-duration opioids in reducing short-term (immediate postoperative), intermediate term (1-30d post-discharge), and chronic (6-12 mo) postoperative pain.

Pain reduction effectiveness of methadone vs short-duration opioids will be compared using repeated measures models to adjust for multiple measures on each subject. Depending on the distribution of NRS, VAS and pain relief data, data will be analyzed as normal, or transformed into an ordinal or other scale.

**Aim 3:** Evaluate major and bothersome short-term (before discharge) and intermediate term (1-30d post-discharge) opioid-related side effects with methadone vs short-duration opioids.

Side effects (respiratory-specific events, composite ORSDS) will be compared between the groups using Chi-squared or Fisher exact test, as appropriate, and using logistic models to adjust for important clinical and demographic covariates.

**Aim 4:** Compare overall recovery after surgery/anesthesia with methadone vs short-duration opioids, as defined by changes in reported Health-related Quality of Life, functional independence, and ability to return to work and normal activity.

Overall recovery will be assessed using chi-square tests for categorical outcomes and t-tests for continuous outcomes as well as a repeated measures model to adjust for multiple time points.

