Statistical Methodology	
Both cohorts are analyzed separately. Demographic data including race, sex, and age will be analyzed using chi-square. Post-discharge opioid use (30d) is compared using Chi-square tests and multiple logistic regression, with opioid group as a predictor and adjusting for covariates. Total pill consumption is compared with a GEE model and Poisson link function. A time-to-event (survival) model will compare time to opioid discontinuation. Opioid use during intraop, in-hospital post-op, and post-discharge periods will be evaluated using appropriate model and data transformation. Pain reduction effectiveness of long- vs short-duration opioids is compared using repeated measures models to adjust for multiple measures on each subject. Side effects will be compared using Chi-squared or Fisher exact tests. Overall recovery will be assessed using chi-square tests for categorical outcomes and t-tests for continuous outcomes as well as a repeated measures model.

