### 2.6.2 Randomization

Subjects in each cohort will be randomized 1:1 to either short-duration or long-duration opioid using randomization tables generated by the hospital Investigational Pharmacy. Each subject is assigned the next number. Anesthesia practitioners are instructed on study procedures, and receive a sealed envelope with Group (drug) assignment and group-specific instructions. To ensure full double-blinding, subjects, investigators, and study team members evaluating patients will be blinded to drug treatment. Dropouts (after treatment) will not be replaced, in case this is not random but outcome-related. Enrollment is increased to account for dropouts.

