### 2.6.3 Preoperative

Patients will complete a questionnaire about current pain, past 7 day average pain, pain interference with activities of daily living, and expected level of postoperative pain (NIH PROMIS-29 Profile v2.0, PROMIS Global Health Scale 1.2, <http://www.nihpromis.org/>). Quality of life indices will be assessed using the Veterans RAND 12-item health survey (VR-12), the Barthel index of activities of daily living, and the Quality of Recovery QoR-15. Demographic data will be recorded. Additional questions will query patients' current employment, level of normal activities, and expectation of time to return to work and normal activities. Demographic data including patient zip codes, employment status, education status, will be recorded. Patient information (demographics, medical history, procedure, medications, pain scores) will be extracted from patient's electronic medical records.

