### 2.6.8 Primary and secondary outcome measures

Primary outcome measure: Total 30d post-discharge home opioid use (number of tablets). This is because surgeons prescribe a variety of post-op opioids (oxycodone, tramadol, oxycodone+acetaminophen, hydrocodone+acetaminophen, codeine+acetaminophen), we avoid any confounding by use of opioid conversion tables, and the most important factor in opioid diversion and misuse is the number of left-over tablets.

Secondary outcome measures:

1. Total 7d post-discharge home opioid use (number of tablets).
2. Total intraoperative non-methadone opioid administration
3. Total PACU opioid administration
4. Total hospital non-methadone opioid administration

Exploratory outcomes:

1. Total day of surgery nonmethadone IV opioid administration
2. Total day of surgery nonmethadone IV and oral opioid administration
3. Total day of surgery opioid administration
4. Postoperative day 1 total IV oral and opioid administration (for short-stay cohort only)
5. Total hospital opioid administration
6. PACU pain scores (NRS) and pain relief score; at time-specific intervals
7. Duration of intraoperative analgesia (median time to request for re-medication with opioid)
8. PACU side effects and adverse events: respiratory depression (4 events occurrence per above), sedation (MOAA/S score), nausea/vomiting (number of events); at time-specific intervals and total
9. PACU duration of stay
10. 7d and 30d total post-discharge home opioid use (in morphine equivalents)
11. 7d and 30d post-discharge pain scores (NRS) and pain relief score; daily
12. Total pain relief (TOTPAR), calculated as the area under the curve of pain relief score vs time
13. 7d and 30d post-discharge opioid side effects (ORSDS); daily, weekly and total (summed and average)
14. Time to cessation of post-discharge opioid use
15. 7d and 30d post-discharge unused opioid tablet count
16. Quality of recovery at 7d, 14d, 21s, 30d, 6 mo, and/or 12 mo (VR-12, Barthel index, QoR-15, functional independence, return to work)
17. Surgeons' opioid prescribing patterns

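### The model named for the 30-day tablet count states no covariates, so surgical procedure, though recorded, enters the plan only as an optional subgroup and precision may be lost

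*Combined protocol and SAP*

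**What the plan says.** Section 2.6.8 declares the outcome: "Primary outcome measure: Total 30d post-discharge home opioid use (number of tablets". For that count, section 2.8 (Aim 1) says "Total pill consumption will be compared using GEE model with Poisson link function", and the synopsis says "Total pill consumption is compared with a GEE model and Poisson link function". Neither sentence gives covariates, the unit of observation or the type of standard error.

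The neighbouring analyses are adjusted. The logistic model for more than 5 pills is fitted "with opioid group as a predictor and adjusting for the important clinical and demographic covariates". A fragment after a page break, "adjusting for the appropriate covariates", reads as the end of the time-to-event sentence. The Aim 3 logistic models are adjusted too. No covariate is listed by name for any of them.

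On procedure, section 2.6.3 says "Patient information (demographics, medical history, procedure, medications, pain scores) will be extracted" from the electronic record. Section 2.4 justifies having two cohorts by possible differences between operations in pain and opioid need. Section 2.8 names procedure only as something that subgroup analysis may look at. Section 2.6.2 describes 1:1 allocation within each cohort "using randomization tables generated by the hospital Investigational Pharmacy" and mentions no procedure strata.

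Section 2.8 also has a general sentence: "Opioid use during intraop, in-hospital post-op, and post-discharge periods will be evaluated using appropriate model and data transformation", depending on how the data are distributed.

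**The concern.** The analysis of the declared primary outcome is specified with less adjustment than the analyses around it. If procedure predicts home opioid use, as the protocol's reason for separating the cohorts suggests, differences between procedures within a cohort stay in the error term of the tablet comparison. Randomization keeps that comparison unbiased. What is at stake is a wider confidence interval than the data could give, when the variable that would narrow it is already being collected.

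There is also a wording fault. Poisson names a distribution, not a link. The usual specification is a log link with a Poisson working variance.

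**Working it through.** **Inputs from the documents.** Control rate above 5 pills 45%, relative risk 65%, 150 evaluable per group (section 2.7).

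**The plan's own figure.** It concerns the binary outcome, not the count. With p1 = 0.45, p2 = 0.65 × 0.45 = 0.2925, mean 0.37125, two-sided 0.05 and 80% power:

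n = [1.960 × √(2 × 0.37125 × 0.62875) + 0.8416 × √(0.45 × 0.55 + 0.2925 × 0.7075)]² / 0.1575² = (1.339 + 0.567)² / 0.0248, which rounds up to 147 per group, or 294 in total.

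This reproduces the stated 300 (power 80.9% at 150 per group). The rounded 30% printed beside it would need 163 per group.

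**Assumptions, because the documents give no tablet mean, spread, procedure mix or procedure-specific rate.**
- Three equal procedure groups.
- Negative binomial counts within each group, size k = 0.8.
- Control rates above 5 pills averaging 45%, with three spreads.
- Relative risk 0.65 within each group.

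Group means m are solved from P(count > 5).

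**Formula.** With robust standard errors and n per arm, the variance of the log rate ratio is close to (W + B)/n without procedure and W/n with it. Each is a sum over the two arms:
- W = average of (m + m²/k), divided by (average m)²
- B = variance of m between groups, divided by (average m)²

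The variance factor is (W + B)/W. With a log link, the ratio of means being estimated is the same with or without the procedure term.

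| Control rates | Control means | Methadone means | W | B | Factor |
|---|---|---|---|---|---|
| 40/45/50% | 6.44, 7.61, 9.03 | 4.02, 4.50, 5.02 | 2.885 | 0.027 | 1.01 |
| 30/45/60% | 4.62, 7.61, 13.04 | 3.17, 4.50, 6.23 | 3.141 | 0.245 | 1.08 |
| 20/45/70% | 3.23, 7.61, 20.12 | 2.39, 4.50, 7.74 | 3.657 | 0.684 | 1.19 |

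For the middle row, the standard error goes from √(3.386/150) = 0.150 to √(3.141/150) = 0.145.

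**Sensitivity.**
- Varying k from 2 to 0.5 gives factors of 1.01, 1.07 to 1.08, and 1.17 to 1.20 for the three spreads.
- If the arms instead differ by one common ratio of mean counts (k = 0.8), the factors are 1.01, 1.11 and 1.24, which is the high end.
- Simulated trials gave about 1.00, 1.04 to 1.10, and 1.13 to 1.19.

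**In terms of power.** An analysis with 80% power moves to Φ(2.802 × √factor − 1.960): about 80% at 1.01, 83% at 1.08 and 86% at 1.19. In patients, 300 adjusted would do the work of about 303, 324 or 357 unadjusted.

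**The case against.** The strongest reply is that the gap is one of silence. The plan never says that the count model is unadjusted, and the unlisted covariates of the other models could include procedure. The general sentence on post-discharge use also leaves the model open. Separate randomization and analysis of the two cohorts already removes some of the difference between operations. Under a mild spread the gain is nil. All of this stands. It makes the point one of specification and precision, and it limits the size. It does not supply the missing term: within a cohort, procedure is pre-specified in no model, and a model left open until the distribution is seen is no substitute for naming it.

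Two stronger readings are tempting.

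**Variance.** A reader might infer that the plan assumes a variance tablet counts cannot have, and so would reject a true null far too often. A pure Poisson count with 45% above 5 has mean 5.4, with only 0.5% of patients taking none, which is implausible. Model-based Poisson errors would then give a type I error of 32% to 79% for negative binomial size 2 to 0.3. But the plan names a GEE. There the Poisson variance is only a working variance, and the usual sandwich errors hold type I error at 5.2% to 5.7% over the same range. No section calls for model-based errors. The fair criticism is that the type of standard error is not written down.

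**Unit of observation.** A reader might also infer that a GEE is pointless on one total per patient. The unit is not stated. Home use is recorded daily (section 2.6.5), and even with one record per patient, a Poisson GEE is a recognised way to obtain robust errors.

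**Conclusion.** The point holds as a loss of precision that is cheap to avoid, not as a threat to validity. The model named for the declared primary outcome states no covariates, and procedure, which is recorded and which the protocol expects to matter, is named only as an optional subgroup. With 150 per arm and three equal procedure groups, adding procedure reduces the variance of the log rate ratio by a factor of about 1.0 under a mild spread and about 1.1 to 1.2 under wide ones. These factors rest on assumed spreads, group sizes and dispersion, since the documents give none. The true gain could be negligible, and the documents do not support a claim of inflated type I error.

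**What to change.** In section 2.8 and the synopsis, replace the count-model sentence with: *Total 30-day tablets per patient will be compared using a log-link count model (Poisson GEE) with robust (sandwich) standard errors, with arm and surgical procedure group as terms.* This also corrects the link wording and settles the unit of observation and the variance estimator.

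Name procedure group as a covariate in the logistic model for more than 5 pills. Define a small number of procedure groups in the plan before unblinding.

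The cost is a sentence in two places, a short list of groups, and a few degrees of freedom. The variable is already collected. A negative binomial model is an equally valid alternative, and stratifying the remaining randomization tables by procedure is optional, since it adds little once procedure is in the model.
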